## 17.2 Sample Size/ Accrual Rate

Melichar et al reported the results of a Phase II clinical trial of alisertib (administered at 50 mg BID for 7 days of a 21 day cycle) monotherapy in women with chemo-resistant metastatic breast cancer. The response rate among the 14 women with triple negative breast cancer was 7.1 % (median PFS: 1.5 months). The response rate among the 26 women with hormone receptor positive disease was 23.1% (median PFS: 7.9 months). Given these results and the expectation that approximately 10% of the patients who will be enrolled onto this trial will have triple negative breast cancer, we anticipate the response rate with alisertib alone will be 20%.

A randomized phase II clinical trial design (proposed by Jung et al) which incorporates a prospective control treatment and a futility stopping rule was chosen to assess whether the tumor response rate with the addition of fulvestrant to alisertib will be greater than that of alisertib alone by at least 20%, when the tumor response rate for alisertib alone is assumed to be 20%. The randomized phase II clinical trial design with a prospective control group proposed by Jung takes into account the interim analysis for futility so that overall design parameters are met.

With a sample size of 45 patients per arm, a one sided alpha=0.15 sequential binomial test of the difference in two independent proportions will have a 85% chance of detecting that the response rate with the addition of fulvestrant to alisertib is at least 20% or greater

than the response rate with alisertib alone, when the true response rate for alisertib alone is 20% or less. The null hypothesis that the difference in tumor responses is less than 20% would be rejected if at least 4 more tumor responses are seen with the combination of fulvestrant and alisertib than with alisertib alone.

It is anticipated that none of the patients who are pre-registered will fail to obtain an ER result from the biopsy of a metastatic lesion. However, some patient may cancel participation prior to registration/randomization or after randomization but prior to the start of assigned treatment and other patients may be found to be ineligible. These patients will be replaced. It is anticipated that an additional 6 patients may be enrolled to account for these situations.

**Futility stopping rule:** If, after the first 28 patients on each treatment arm have been enrolled and completed at least 6 cycles of treatment, the difference in the number of tumor responses between the treatment arms is one or fewer, enrollment will be halted and the DSMB will be consulted to formulate patient treatment recommendations.

Other Considerations that might lead to early closure: Toxicity, patterns of treatment failure observed in this study and scientific discoveries or changes in standard care will be taken into account in any recommendation to the DSMB to terminate this trial earlier than anticipated.

- 17.2.1 Crossover: Patients who are assigned to alisertib only arm who progress may choose to receive the combination of fulvestrant and alisertib. We anticipate that at least 14 (if there is no signal that combination therapy may be more beneficial) and as many as 22 patients will choose to receive combination therapy. As such, a 95% binomial confidence interval will be constructed for both the tumor response rate and clinical benefit rate during crossover treatment.

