### 17.1 Assessing the impact of adding fulvestrant to alisertib

#### 17.1.1 Primary Endpoint

The primary endpoint is tumor response rate with initial treatment. That is,

- Arm 1: Tumor response rate is defined as 100% times the number of patients who meet the criteria for CR or PR (using RECIST criteria version 1.1) on 2 consecutive evaluations approximately 8 weeks apart during treatment with alisertib monotherapy divided by the number of patients who started alisertib monotherapy.
- Arm 2: Tumor response rate is defined as 100% times the number of patients who meet the criteria for CR or PR (using RECIST criteria version 1.1) on 2 consecutive evaluations approximately 8 weeks apart

during treatment with combination of alisertib and fulvestrant divided by the number of patients who started treatment with the combination of alisertib and fulvestrant.

The study will test the hypothesis that the addition of fulvestrant to alisertib will increase the tumor response rate over that of alisertib alone by at least 20%.

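### The null written in Section 17.2 (a gain of less than 20 points) does not fit the decision rule, which tests for no difference and rejects at an 8.9-point excess

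*Combined protocol and SAP*

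**What the plan says.** Section 17.1.1 gives the study hypothesis: that adding fulvestrant "will increase the tumor response rate over that of alisertib alone by at least 20" per cent.

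Section 17.2 gives the design:

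- **Control rate.** The plan says "we anticipate the response rate with alisertib alone will be 20" per cent.
- **Size and test.** "With a sample size of 45 patients per arm, a one sided alpha=0.15 sequential binomial test" of the difference in two proportions, which "will have a 85% chance of detecting" a gain of 20 points or more when the alisertib rate is 20% or less.
- **Final rule.** "The null hypothesis that the difference in tumor responses is less than 20% would be rejected if at least 4 more tumor responses" are observed on the combination than on alisertib alone.
- **Futility rule.** After 28 patients per arm, enrolment halts if the arms differ by one response or fewer.

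No section of the plan states a null of no difference.

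**The concern.** A rule that rejects a null of a gain below 20 points should require an observed gain above 20 points. This one requires 8.9. Either the cut-off or the null is wrong, and the text does not say which.

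The hypothesis sentence fixes what a positive primary result may claim. Read literally, rejection means that fulvestrant adds at least 20 points to the response rate. If the rule is really a superiority test at one-sided 0.15, rejection supports only a response rate higher than with alisertib alone.

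The written text also contradicts itself. The rejection probability varies continuously with the true gain. One test therefore cannot have at most a 15% chance of rejecting at every gain below 20 points and an 85% chance at exactly 20 points.

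**Working it through.** **Inputs (Section 17.2).** Control rate 20%; target gain 20 points (40% on the combination); 45 per arm; one-sided alpha 0.15; power 85%; interim at 28 per arm; final rejection at 4 or more extra responses. The futility difference is taken as combination minus alisertib, the same direction as the final rule. This is an assumption, because the text gives no sign.

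**Rule.** Let D1 be the difference in responses at 28 per arm and D the difference at 45 per arm (17 more per arm). The trial continues if D1 ≥ 2 and rejects if D ≥ 4:

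P(reject) = Σ over d ≥ 2 of P(D1 = d) × P(D2 ≥ 4 − d),

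where D2 is the difference among the additional 17 per arm. Each distribution is the exact difference of two independent binomials.

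**Step 1: reproduce the plan's figures.**

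| True rates (alisertib vs combination) | P(reject) | Plan's figure |
|---|---|---|
| 20% vs 20% | 0.1466 | alpha 0.15 |
| 20% vs 40% | 0.8501 | power 85% |

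Both match. The boundaries were therefore built for a null of no difference and an alternative of 20 points. If the futility difference is read as unsigned, the values are 0.148 and 0.853, so the conclusion does not depend on that assumption.

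**Step 2: convert the cut-off.** 4/45 = 0.0889, or 8.9 points, less than half of 20.

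**Step 3: apply the same rule to the null as written.** Each row below has a true gain under 20 points, so each rejection would be an error under that null (control rate 20%).

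| True gain (points) | P(reject) |
|---|---|
| 0 | 0.147 |
| 5 | 0.320 |
| 10 | 0.526 |
| 15 | 0.714 |
| 19.9 | 0.848 |

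The type I error for the written null therefore approaches 0.85.

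**Step 4: what the written null would require.** For a one-sided 0.15 test of a gain of 20 points or less at 45 per arm and a 20% control rate, the cut-off k must satisfy P(D ≥ k | 20% vs 40%) ≤ 0.15. At k = 13 the probability is 0.205; at k = 14 it is 0.144. So 14 extra responses are needed (14/45 = 31.1 points). Under that cut-off the chance of rejecting at a true 40% versus 20% is only 0.144.

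**Step 5: a result exactly on the boundary.** Take 13/45 versus 9/45. The difference is 0.0889. The Wald standard error is √(0.2889 × 0.7111/45 + 0.20 × 0.80/45) = 0.0901. One-sided 85% bounds are 0.0889 ± 1.036 × 0.0901, or −0.5 and 18.2 points. The plan's rule would reject the null of a gain under 20 points here, although even the upper bound is below 20.

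**The case against.** The strongest reply is that only the label is wrong. The sample size, interim rule and cut-off deliver the stated alpha and power, and no enrolment, stopping or rejection decision would change. An 85% error near 20 points is simply the planned power seen through a misworded null. It is not an inflated false-positive rate for superiority. The 14-response figure likewise describes a test nobody intended. The primary objective in Section 2.1 and the opening of Section 17 speak only of assessing the impact of fulvestrant, and Section 1 speaks of superior outcomes, all without a 20-point threshold. No section prescribes the sentence to be reported after rejection.

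Much of this stands. The design is sound, the 85% figure belongs to the wording, and the overclaim arises only if the text is applied as written. But none of those other sections states a null of no difference, and Sections 17.1.1 and 17.2 are the operative statistical text. A statistician may guess the intention; a reader of the primary result should not have to.

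A second reply concerns the correction. With a null of no improvement, exact alpha stays within 0.15 only while the common response rate is near 20% or lower. It passes 0.15 at about 21%, is 0.172 at 30% and peaks at 0.188 at 50%. This is correct, and the corrected text should keep the plan's existing limit to control rates of 20% or less.

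**Conclusion.** The concern holds. The plan has put its alternative where the null belongs. The existing rule tests for no difference with exact one-sided alpha 0.147 and power 0.850 at 20% versus 40%. For the null as written, the error rate reaches about 0.85, and rejection can follow an observed excess of only 8.9 points. These figures assume a 20% control rate, 28 then 45 patients per arm as planned, independent binomial responses, and a futility difference taken as combination minus alisertib. The error is confined to wording, but it governs what the primary analysis may conclude, so it must be corrected before results are reported.

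**What to change.** In Sections 17.1.1 and 17.2:

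1. State the null as: the combination's response rate is no higher than that of alisertib alone. State the alternative as a 20-point gain, 20% versus 40%.
2. Remove the gain of at least 20% as the hypothesis under test, and keep it only as the effect the trial is powered to detect.
3. Attach one-sided alpha 0.15 and 85% power to the existing boundaries, with the present condition that the alisertib rate is 20% or less.
4. State that the futility difference is combination minus alisertib.
5. State that rejection supports only a higher response rate than alisertib alone.
6. Report the observed difference with a confidence interval, so that readers can judge whether 20 points is plausible. Section 17 specifies intervals for the clinical benefit rate and the crossover response rate but none for the primary difference.

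The cost is protocol wording only. The 45 per arm, the interim rule and the 4-response cut-off are unchanged; the permitted conclusion becomes more modest.

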### 17.3 Stratification Factors

This study will use the Pocock and Simon dynamic allocation procedure to allocate an equal number of patients to each of the treatment strategies. This procedure will balance the marginal distributions of the stratification factors, clinical endocrine resistance and ER status, between these treatment strategies.

- Clinical Resistance to Endocrine Therapy:
  - 1= Primary endocrine resistance- recurrence within the first 2 years of adjuvant endocrine therapy, or progression within the first 6 months of initiating first-line endocrine therapy for MBC
  - 2= Secondary endocrine resistance- recurrence during Years 2-5 of adjuvant endocrine therapy (or within 12 months of completing adjuvant endocrine therapy) or progression occurring 6 or more months after initiating endocrine therapy for MBC.
- ER findings from registration biopsy
  - 1 = ER positive ( $\geq 10\%$  staining)
  - 2 = ER weakly positive (1 to 9.9% staining) or ER negative (0% staining)
- Prior therapy with a CDK 4/6 inhibitor (palbociclib, ribociclib or abemaciclib)
  - 1=yes

2=no

## 17.4 Analysis of Secondary Endpoints

17.4.1 For each treatment arm, the distribution of PFS times, overall survival times, and duration of response will be estimated using the Kaplan-Meier method.

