## 2. OBJECTIVES

### 2.1 Primary Objective

To assess the impact on objective tumor response rate (using RECIST criteria) with the addition of fulvestrant to alisertib in women with endocrine resistant, advanced, estrogen receptor positive breast cancer.

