### 2.2 Secondary Objectives

- 2.2.1 To evaluate the safety profile of each treatment regimen
- 2.2.2 To assess the impact on median progression-free survival with the addition of fulvestrant to alisertib
- 2.2.3 To obtain estimated tumor response rate and the median progression-free survival time during alisertib and fulvestrant treatment in the cohort of patients who progress during alisertib monotherapy, and crossover to receive the combination of alisertib and fulvestrant.

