			Day 1 of each treatment cycle* 	At PD or discontinuation of alisertib	Day 1 of each treatment cycle 	At PD or discontinuation of alisertib + fulvestrant
Tests and procedures	≤28 days prior to Pre-registration					
Chemistry group – Sodium – Potassium – BUN – Creatinine – Calcium – Glucose – Albumin – AST – ALT  – Alkaline Phosphatase – Total Bilirubin 		X	X	X	X	X
Tumor measurement 	X		X	X	X 	X
Alisertib			X		X	
Fulvestrant					X 	
Patient Medication Diary (Appendix III) 			X	X	X	X

 FOR CYCLE 1 DAY 1 ONLY: If either to the following holds: (1) total bilirubin >1.5 x ULN or (2) Alanine transaminase >5 x ULN, then the patient should not begin protocol treatment. The patient should go off study and will be considered a cancel (see Section 6.4.8).

 The same imaging modality (CT scan, CT component of a PET/CT, or MRI) must be used throughout the study. Baseline imaging should be obtained ≤28 days prior to Registration. Tumor measurements are to be done at the completion of Cycles 2, 4, 6, etc., for first two years or until disease progression, whichever is first. Patients who have achieved complete response, partial response, or stable disease for ≥2 years may reduce imaging to every fourth cycle.

 Scans are not required Day 1 of Cycle 1 of fulvestrant and alisertib. The scans taken at the time of progression on alisertib will serve as the baseline scan for the fulvestrant and alisertib treatment phase of the study.

 Fulvestrant will be given on Day 1 of every cycle and on Day 15 (±1 day) of Cycle 1 only.

 The diary must begin the day the patient starts taking the medication and must be completed per protocol and returned to the treating institution at the completion of each cycle of treatment (approximately every 28 days). Compliance must be documented in the medical record by any member of the care team.

			Alisertib Treatment Phase		For patients who meet requirements set out in Section 6.1.2 Alisertib + Fulvestrant Treatment Phase	
Tests and procedures	≤28 days prior to Pre-registration	Pre-registration period (spans the first 28 days after pre-registration) 	Day 1 of each treatment cycle* 	At PD or discontinuation of alisertib	Day 1 of each treatment cycle 	At PD or discontinuation of alisertib + fulvestrant

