## 17. STATISTICAL CONSIDERATIONS AND METHODOLOGY

The aims of this clinical trial include assessing the impact of adding fulvestrant to alisertib in terms of clinical benefit (response rate and progression-free survival) and safety.

Among the patients who are assigned to alisertib monotherapy (Arm 1) who progress and choose to receive the combination of fulvestrant and alisertib, the primary aims are to examine response and the differences in time to progression with alisertib and that with fulvestrant and alisertib.

Initial treatment refers to alisertib alone for those randomized to Arm 1 and alisertib with fulvestrant for those randomized to Arm 2. Crossover treatment only applies to patients who progress during treatment with alisertib alone on Arm 1.

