### 17.4.2 Clinical benefit rate

For initial treatment in each arm, the clinical benefit rate at 24 weeks will be defined as the proportion of patients who completed 6 cycles of treatment without documentation of disease progression. A 90% confidence interval for the CBR will be constructed using the Duffy-Santner approach to take into account the sequential nature of the study design.

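### The plan asks how adding fulvestrant affects PFS but specifies only a Kaplan-Meier estimate per arm, with no between-arm effect and no PFS confidence interval

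*Combined protocol and SAP*

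**What the plan says.** Section 2.2.2 sets the objective: "To assess the impact on median progression-free survival with the addition of fulvestrant to alisertib". Section 17 opens with the same aim and names PFS in it: "assessing the impact of adding fulvestrant to alisertib in terms of clinical benefit (response rate and progression-free survival) and safety". Section 17.1.2.3 defines PFS as running from randomization to progression or death from any cause.

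The planned analysis is the single sentence of Section 17.4.1: "For each treatment arm, the distribution of PFS times, overall survival times, and duration of response will be estimated using the Kaplan-Meier method". Nothing else in the document adds a log-rank test, a Cox model, a hazard ratio, a difference in medians or any other PFS contrast. No confidence interval is specified for PFS, even within an arm.

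Other endpoints get more. For response, Section 17.1.1 states: "The study will test the hypothesis that the addition of fulvestrant to alisertib will increase the tumor response rate over that of alisertib alone", and Section 17.2 supplies a between-arm test. For clinical benefit rate, Section 17.4.2 states: "A 90% confidence interval for the CBR will be constructed using the Duffy-Santner approach". For the crossover phase, Section 17.2.1 plans 95% binomial intervals for response and clinical benefit.

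**The concern.** The wording of the objectives separates a comparison from an estimate. The primary objective, "To assess the impact on objective tumor response rate (using RECIST criteria) with the addition of fulvestrant to alisertib", has the same form as 2.2.2 and is analysed as a difference between arms. Objective 2.2.3, for the crossover cohort, is worded differently: "To obtain estimated tumor response rate and the median progression-free survival time during alisertib and fulvestrant treatment". So 2.2.2 reads as a comparison, yet 17.4.1 treats it as estimation within each arm.

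PFS is secondary and unpowered here, so what it can contribute is an estimate with its uncertainty. Without that, a reader has two medians side by side and may take a chance gap for a fulvestrant effect, or dismiss a real one. Because the plan is silent, the choice of effect measure, confidence level and adjustment would also be made after the data are seen.

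**Working it through.** **The plan's own figures.** Section 17.2 gives 45 per arm, one-sided alpha 0.15 and 85% power for 20% against 40% response, with a futility look at 28 per arm. An exact two-stage calculation (continue if the combination leads by at least 2 responses at 28 per arm, reject if it leads by at least 4 at 45 per arm) gives alpha 0.147 and power 0.850. The design reproduces, but it concerns response only. No event count, alpha or power is stated for PFS, so there is no PFS figure to reproduce.

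**How far two medians drift apart by chance.** Inputs from the document:
- 45 per arm (17.2).
- A 7.9-month median, from the earlier single-agent trial's hormone-receptor-positive cohort of 26 (17.2).
- Scans every two 28-day cycles (11.1): "Tumor measurements are to be done at the completion of Cycles 2, 4, 6, etc., for first two years". One scan step is 2 × 28 = 56 days, or 1.84 months; two steps are about 3.7 months.

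Assumptions: exponential PFS with the same true median in both arms, and uniform censoring at 12 to 36 months. Simulated share of trials in which the observed medians differ by at least the stated gap:

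| Timing of progression | ≥ 1.84 months | ≥ 3.7 months |
|---|---|---|
| Continuous time, or scans up to 4 days off schedule | about 45% (43% to 45% across runs) | about 13% |
| Every progression on an exact 8-week grid | about 70% | about 26% |

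The first row is the one to quote. On a perfect grid, medians can differ only in whole steps, so the 70% means little more than that the medians were not tied. The protocol does not produce such a grid: cycles are 28 ± 3 days (6.1), assessments may be up to 4 days early (11.1, footnote 3), and deaths and symptomatic deterioration (12.3.4) are not tied to scans.

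**What a hazard ratio would deliver.** With 1:1 allocation and d events, SE(log HR) = 2/√d, and the 95% interval is the estimate times or divided by exp(1.96 × 2/√d):

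| Events (assumed) | 1.96 × 2/√d | Factor |
|---|---|---|
| 90 | 0.413 | 1.51 |
| 71 | 0.465 | 1.59 |
| 56 | 0.524 | 1.69 |
| 47 | 0.572 | 1.77 |

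The last two rows matter because of the futility rule in 17.2, which halts enrolment if the difference at 28 per arm is one response or fewer. With a 20% response rate in both arms, that probability is exactly 0.69. If fulvestrant adds nothing to response, a trial of about 2 × 28 = 56 patients is therefore the likelier outcome, and 47 to 56 events is the matching assumed range.

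**Does crossover get in the way?** No. Under 6.1.2 it begins only after progression on alisertib alone, so time from randomization to first progression or death remains a randomized comparison.

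**The case against.** The strongest reply is that this is a recognisable phase II choice: only response is formally compared, and secondary efficacy endpoints are summarised by arm. The interval in 17.4.2 fits that pattern, since it is per arm and not between arms. Objective 2.2.2 is worded in medians, which Kaplan-Meier curves supply. This stands in part: it makes rewording the objective a legitimate remedy. It does not remove the mismatch, because 2.2.2 and the Section 17 aim ask for the impact of adding fulvestrant, and even the per-arm medians have no planned interval.

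Several stronger readings are tempting, and the documents do not support them:
- A reader might infer that a between-arm PFS test is required, or that the trial is underpowered for PFS. The plan makes no PFS power claim, and nothing here calls for a test.
- A reader might infer that chance gaps of a full scan step occur in 70% of trials. That holds only if all progressions fall on an exact 8-week grid.
- A reader might argue for covariate adjustment because it raises power. That would need prognostic strengths and subgroup shares for which the documents give no PFS figures, and power is the wrong criterion when no test is claimed. The case for adjustment is simply that the factors in 17.3 drive the allocation and are already recorded.

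**Conclusion.** The omission is certain and can be checked on the page: a stated secondary objective cannot be answered, with a measure of uncertainty, by following the plan as written. It should be corrected. It does not touch the primary response comparison or its operating characteristics.

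The size is less certain. The figures of about 45% and 13% rest on exponential PFS, a 7.9-month median borrowed from another trial, 45 per arm and the assumed censoring. They also describe a trial that reaches full enrolment, which under no response effect is the less likely path. The hazard ratio interval depends on event counts that the documents do not give. It would be wide in every case, which is a reason to show it.

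**What to change.** Add to Section 17.4.1:
- A Cox hazard ratio for PFS as defined in 17.1.2.3 (randomization to first progression or death), with a stated confidence level.
- Adjustment by covariates for the three allocation factors in 17.3 (endocrine resistance, ER status, prior CDK 4/6 inhibitor), with the unadjusted hazard ratio beside it.
- Each arm's median with its interval, to match the wording of 2.2.2.
- A label that these results are supportive and unpowered, with no test claimed.

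Alternatively, if PFS is meant to be descriptive, reword 2.2.2 and the Section 17 aim as per-arm estimation, in the manner of 2.2.3, and report each median with its interval. That is sufficient by itself.

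The cost is a few lines of text and a few more model runs, with no added patients, visits or data. The drawback is that adjusted estimates will be slightly less stable because the ER-low group is small: 0.10 × 90 = 9 patients at the 10% expected in Section 1, or 0.20 × 90 = 18 at the upper figure of 20% in Section 3.5.
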